8.2. Secondary Objective Measurement Variables

- Physical exploration:
 - BMI
 - Blood pressure
 - Weight
 - Abdomen perimeter

- Laboratory tests:
 - HbA1c
 - Haemoglobin
 - Triglycerides
 - Total, LDL and HDL cholesterol
 - PSA
 - Total testosterone
 - Fasting glycaemia
 - C-Reactive Protein

8.3. Adverse Event Recording

Any adverse events experienced by the patients in the course of the study will be recorded.

8.4. Study Visits

8.4.1. Baseline Visit (Month 0)

The patients should be explained the programme in detail before entering the study. Additionally, the following will be obtained and recorded:

- Patients will be confirmed to satisfy all inclusion and exclusion criteria
- Patients will sign the informed consent
- Demographic variables: initials, date of birth, race
- Current clinical history: including the prostate cancer current stage and the treatments received up to the moment of entering the study
- Record of concomitant medications
- Record of concomitant diseases
- Physical examination: including systolic and diastolic blood pressure determination (all the investigators shall use the same model of sphygmomanometer), measurement of the abdominal perimeter (all the investigators shall use the same tape measure), and weight
- Analytical determinations: Glycaemia, HbA1c, Haemoglobin, Lipid profile: total cholesterol, HDL-cholesterol, LDL-cholesterol and triglycerides), Thyroid hormones (TSH), PSA, Total testosterone and C-Reactive protein
- Assessment of Metabolic Syndrome
- Record of the treatment with quarterly LHRH analogues
- Record of adverse events considered to be associated with the LHRH analogues, including local tolerability of the injection

8.4.2. Follow-up Visits (Month 6 and Month 12)

The following information should be collected and recorded in the CRFs at each visit:

- Physical examination: including measurement of systolic and diastolic blood pressure, measurement of the abdominal perimeter, and weight
- Analytical determinations: Glycaemia, HbA1c, Lipid profile including: total cholesterol, HDL-cholesterol, LDL-cholesterol and triglycerides), Thyroid hormone (TSH), PSA, Total testosterone and C-Reactive protein
- Record of concomitant medications
- Assessment of Metabolic Syndrome
- Record of treatment with quarterly LHRH analogues
- Record of adverse events considered to be associated with the LHRH analogues, including local tolerability of the injection

8.5. Study Termination by a Patient

Some of the reasons why a patient should terminate the study are described below:

- Patient withdraws his consent.
- Investigator's decision.
- Patient transferred or lost to follow-up.
- Adverse event.
- Lack of adherence.

If a patient dropped out from the study, the reasons should be recorded in the CRF.

8.6. Study Termination

Ipsen has the right to terminate this study at any time. The reasons leading to such termination include, but are not limited to, the following:

- The incidence or the severity of adverse events either in this study or in other studies are indicating potential risks for the patients.
- The recruitment is not sufficient to satisfy the objectives of the study.
- The primary and/or secondary objectives of the study have been reached.

8. STATISTICAL CONSIDERATIONS

8.1. Classification and Definitions of the Subjects of the Study

Pre-selected centre:	Centre requested to participate in the study and verified to be currently following-up patients who might be candidates to entering the study (this involves both participating and not-participating centres)
Participating centre:	Centre that has accepted to participate in the clinical study and completed the patients screening records
Participating subject:	Subject who has been thoroughly informed about the study and who has given his/her written informed consent for participation (prior to initiating any of the study procedures)
Treated subject:	Participating subject treated with at least one dose of the study drug

Subject who has completed the study:	Treated subject who has completed all of the study assessments
Dropout:	Treated subject who has not completed the study and/or the treatment

8.2. Definitions of Analysis Populations

Included and treated population:	All treated subjects
Complete population:	All treated subjects paying the Month 12 end visit

9.2.1. Analysis Populations

The primary analysis will be performed on the whole of the population, Additionally, the analysis will be repeated on the included and treated population.

Analysis of the safety data will be performed on the treated population.

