9.2.2. Subject Allocation and Reasons for Exclusion from Analyses

The instructions for allocation of subjects to each of the analysis populations will be defined and documented in the course of a data review meeting.

Those subjects in whom one or more of the violations and/or deviations below occurs may be excluded from analysis:

- violation of the inclusion and/or exclusion criteria
- having received no study drug whatsoever
- not adhering to the study drug as they should

- taking banned medications
- committing deviations regarding treatment administrations
- having had no initial or post-initial assessment of the primary results

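### The primary analysis set carries a label the protocol does not define, the repeat cannot add patients without a Month 12 status, and exclusions are left to an undated meeting

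*Protocol*

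**What the plan says.** The protocol section on definitions of analysis populations (8.2) gives two sets. The included and treated population is every treated subject, a treated subject being: "Participating subject treated with at least one dose of the study drug". The Complete population is: "All treated subjects paying the Month 12 end visit".

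Section 9.2.1 then assigns the analyses: "The primary analysis will be performed on the whole of the population, Additionally, the analysis will be repeated on the included and treated population".

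Section 9.2.2 governs exclusions. On when the rules are made: "The instructions for allocation of subjects to each of the analysis populations will be defined and documented in the course of a data review meeting". On who can be removed: "Those subjects in whom one or more of the violations and/or deviations below occurs may be excluded from analysis". The list that follows includes poor adherence, deviations in treatment administration, "taking banned medications" and "having had no initial or post-initial assessment of the primary results". It is not tied to either population.

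Sections 9.3.1 and 9.4.4 fix the primary method: a two-sided 90% Newcombe method 10 interval for paired data, study completion minus study initiation. Success requires an upper limit below +5 points. The sample size section plans 500 pairs and recruits 556 to allow for 10% dropout.

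**The concern.** Three things the protocol fixes do not fit together.

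- **Label.** The set named for the one confirmatory test is not a defined set. Read literally it is everyone; read by elimination it is the Complete population.
- **Method against population.** A paired interval needs a baseline and an end status. A patient with no Month 12 status forms no pair, whichever population is named. The repeat on all treated subjects therefore cannot show whether dropout matters, which is what a reader would expect it to show.
- **Exclusions.** Removal is optional, and the allocation rules are written at a meeting with no date. No medication is banned anywhere in the protocol; section 7 only asks that concomitant medication be reported. The Complete population as defined has no exclusion for adherence or administration. The study is open and has no control group, and MS is assessed at baseline, Month 6 and Month 12, so nothing in the text prevents the meeting from knowing who converted.

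Success means showing that no large increase occurred. Each converter lost or removed moves the result toward success.

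**Working it through.** **1. The plan's own figure.** Inputs from the sample size section: difference 0.020, discordant proportion 0.070, both-yes proportion 0.290, one-sided 5%, margin 0.050.
- Gains: (0.070 + 0.020)/2 = 0.045. Losses: (0.070 − 0.020)/2 = 0.025.
- Simulating 500 pairs with the Newcombe method 10 upper limit gives 80.0–80.1% power, against 80% stated.
- 500/0.9 = 555.6, rounded up to 556.

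The plan is therefore sized on patients who have both assessments. This supports reading the primary set as the Complete population.

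**2. Formula.** Let e = MS at both times, f = gains, g = losses, h = neither, n = e + f + g + h. Then p1 = (e + f)/n is end prevalence, p2 = (e + g)/n is baseline prevalence, and d = (f − g)/n. With z = 1.645, u1 is the Wilson upper limit for p1 and l2 the Wilson lower limit for p2. φ = (eh − fg − n/2)/√[(e+f)(g+h)(e+g)(f+h)].

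Upper limit = d + √[(u1 − p1)² − 2φ(u1 − p1)(p2 − l2) + (p2 − l2)²].

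The cell counts below are illustrative assumptions: 30% baseline MS and, in the base case, about the planned gains and losses.

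**3. Base case, 500 pairs.** e = 138, f = 22, g = 12, h = 328.
- p1 = 0.320, u1 = 0.3552; p2 = 0.300, l2 = 0.2674; φ = 0.837.
- d = 10/500 = 0.0200. Upper limit = 0.0200 + 0.0195 = 0.0395, or 3.95%: success.

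**4. Discretionary exclusion.** e = 138, f = 28, g = 12, h = 322.
- d = 16/500 = 0.0320. Upper limit = 0.0320 + 0.0210 = 5.30%: failure.
- Remove two converters (f = 26, n = 498): d = 14/498 = 0.0281. Upper limit = 0.0281 + 0.0206 = 4.87%: success.

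Two exclusions in 500 reverse this near-margin result.

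**5. Dropouts.** Add 56 patients (556 − 500) to the base case, 17 with MS at baseline and 39 without.

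| Gains among the 56 | Losses among the 17 | Upper limit | Result |
|---|---|---|---|
| 2 | 1 (similar to completers) | 3.80% | success |
| 7 | 0 | 4.97% | success |
| 8 | 0 | 5.17% | failure |
| 8 | 1 | 5.01% | failure, just |
| 8 | 2 | 4.86% | success |
| 9 | 2 | 5.06% | failure |

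Eight gains and no losses is a net change of 8/56 = +14.3 points, against +2.0 in completers. Cells closer to the plan's both-yes proportion (145 both, 23 gains, 13 losses; 18 of 56 dropouts with MS at baseline and keeping it) put the turning point at 7 gains, with an upper limit of 5.01%.

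**6. True increase.** With completers at +2 points and 10% dropouts, an overall +5 needs a net change among dropouts of (5 − 0.9 × 2)/0.1 = +32 points.

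**The case against.** The label may be no more than a slip for the Complete population. Only two sets exist, the other is named for the repeat, and the sample size agrees. That is the likely reading, but the text does not state it, and the literal reading is the opposite.

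A separate SAP is announced. Missing-data rules and detailed allocation are often settled there, so the absence of an imputation rule from the protocol is not counted here. What remains is that the protocol itself pairs a population with a method that cannot use all of it.

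Four stronger readings are tempting and not supported:

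- *The repeat simply returns the completer result.* It may restore patients with Month 12 data who were removed for deviations, so the two analyses can differ. A Month 6 status would also meet the loose wording on post-initial assessment, so a stated rule could bring some dropouts in.
- *Expected dropout is twice the margin, so dropout threatens the result.* 10% is a share of patients and 5 points is a difference in prevalence; their ratio says little. A reversal needs dropouts to gain about seven times as much, net, as completers (14.3/2.0). Nothing in the protocol supports that difference or its direction. Nor need all 56 be missing, because a dropout is defined as: "Treated subject who has not completed the study and/or the treatment". A patient who stops treatment but attends Month 12 already belongs to the Complete population.
- *Exclusions will be made with knowledge of the outcome.* The open design allows this; the protocol does not say it will happen.
- *Success should require both analyses.* That replaces the decision rule of section 9.3.1 and can only lower power from the planned 80%.

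**Conclusion.** The point holds as a matter of definition and control, and should be corrected. The primary set is not identifiable from the text, though the Complete population is most plausible. The repeat is no check on dropout under the paired method. The exclusion rule is open-ended, and one of its criteria has no content.

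The exclusion route needs the fewest patients: in the illustration two converters in 500 move the upper limit from 5.30% to 4.87%. This assumes a result close to the margin. The dropout route needs a strong contrast between dropouts and completers, about 8 of 56 converting with no losses. If dropouts resemble completers the upper limit is about 3.8% and success stands. All cell counts are assumptions; only the planned proportions, the margin, the method and the 10% dropout come from the protocol.

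**What to change.** - **Section 9.2.1:** name the Complete population as primary, stated as treated subjects with MS status at both baseline and Month 12.
- **Section 9.2.2:** delete the criterion on banned medications. Replace the optional exclusions with objective criteria, say which population each applies to, and have them signed off before Month 12 MS status is derived.
- **Repeat analysis:** describe it as a supportive sensitivity analysis that includes treated patients without Month 12. One option is multiple imputation of the Month 12 components from baseline and Month 6 components, with a tipping-point display of net conversion among dropouts. One sentence in the protocol is enough, with detail in the SAP.
- **Section 9.3.1:** leave the decision rule unchanged, on the primary analysis alone.

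The cost is a few lines of text, modest programming on data already collected, and a slightly wider supportive interval. Sample size and the power of the primary test do not change.

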9.2.2. Subject Allocation and Reasons for Exclusion from Analyses

The instructions for allocation of subjects to each of the analysis populations will be defined and documented in the course of a data review meeting.

Those subjects in whom one or more of the violations and/or deviations below occurs may be excluded from analysis:

- violation of the inclusion and/or exclusion criteria
- having received no study drug whatsoever
- not adhering to the study drug as they should

- taking banned medications
- committing deviations regarding treatment administrations
- having had no initial or post-initial assessment of the primary results

8.3. Sample Size Determination

If we assume:

- 1) metabolic syndrome (MS) prevalence = 30% at study initiation,
- 2) that such prevalence will increase by 2% along the study,
- 3) that 5% of prevalence increase is clinically not significant,
- 4) that $\alpha = 5\%$ (unilateral) and power = 80%, and that we mean to demonstrate that the increase of MS prevalence will be lower than 5% (non-inferiority study)

Using 500 subjects, the upper limit of the unilateral confidence interval (CI) observed of 95% will be expected to be lower than 0.050 with a power of 80% when the expected difference, $p_T - p_S$, D_1 , is 0.020 and the proportion of discordants, $h = p_{10} + p_{01}$, is 0.070, and the proportion yes in both cases, p_{11} , is 0.290. The results are based on 5000 simulations that used the Newcombe-Wilson's score method to produce the confidence interval (Newcombe RG (1988): *Improved confidence intervals for the difference between binomial proportions based on paired data*. *Statistics in Medicine* 17:2635-2650).

Considering a 10% dropout rate, the final sample size is $500/0.9 = 556$ subjects. The recruitment of 556 subjects from some 60 Spanish centres has been devised. Each of the centres will be requested to enlist them following a chronological order based on the date of the first visit carried out at the centre.

Assuming this sample size, the MS prevalence will be estimated with a precision of 0.038 (for a 5% bilateral alpha).

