If we assume that the increased prevalence of the metabolic syndrome will be less than 5%, that 1% of the subjects with baseline MS will not show it at the end of the study, and having established an alpha value of 5%, 500 patients are necessary to have a statistical power of 80%. If we assume 10% of dropouts, 556 subjects are necessary.

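### The sample-size inputs cannot all hold: h = 0.070 with p11 = 0.290 does not fit the plan's 30% baseline and 1% reversion, so section 7's claim that 500 patients are needed for 80% power does not follow

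*Protocol*

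**What the plan says.** Two places in the protocol give the sample-size assumptions.

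- Section 7 (Previous Determination of the Sample Size) assumes a 30% prevalence of metabolic syndrome (MS) at the start and a further 2% during the study. It adds "that 1% of the subjects with baseline MS will not show it at the end of the study". With alpha at 5%, it concludes that 500 patients are needed for 80% power, or 556 after 10% dropout.
- Section 8.3 (Sample Size Determination) repeats "metabolic syndrome (MS) prevalence = 30% at study initiation", again with a 2-point rise, and sets one-sided alpha at 5% and a 5-point margin. Among its simulation inputs, D1 is put at 0.020 and p11 at 0.290. For h, the sum of the two discordant cells, the text reads "is 0.070, and the proportion yes in both cases". Power was found by simulating Newcombe's paired score interval 5000 times. With 500 subjects the stated power is 80%.

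Section 8.3 does not repeat the 1% reversion figure. Neither section gives a basis for h = 0.070 or describes it as a safety allowance.

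**The concern.** In a paired before-and-after comparison, the difference and the discordant proportion together fix both off-diagonal cells of the 2x2 table. Adding p11 fixes both prevalences. The protocol states more quantities than the table has free cells, so they can be checked against each other, and they do not agree.

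This matters because discordance is the input that drives power in this design, and the sample-size statement supports the study's only confirmatory claim: that the rise in prevalence is below 5 points (sections 9.3.1 and 9.4.4). As written, a reader cannot tell which discordance the study is powered for. Section 7 also presents 500 as necessary under assumptions that do not require it.

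**Working it through.** **Inputs.** From section 8.3: baseline 0.30, D1 = 0.020, h = 0.070, p11 = 0.290, margin 0.05, one-sided alpha 5%, n = 500. From section 7: 1% reversion. From section 9.3.1: Newcombe's method 10 with a 90% two-sided interval, where success means an upper limit below 5%.

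**Step 1: reproduce the stated power.** Write gain for MS at the end only and loss for MS at baseline only.

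- gain = (h + D)/2 = (0.070 + 0.020)/2 = 0.045
- loss = (h − D)/2 = (0.070 − 0.020)/2 = 0.025

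With p11 = 0.290, n = 500 and z = 1.645, 400,000 multinomial samples give an upper limit below 0.05 in 80.2% of cases. Five runs of 5,000 samples, the protocol's own number, gave 80.0% to 81.1%. The stated 80% reproduces. So does the dropout step: 500/0.9 = 555.6, rounded up to 556.

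**Step 2: what those inputs imply.**

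- Baseline prevalence = p11 + loss = 0.290 + 0.025 = 0.315, against 0.30 stated.
- End prevalence = p11 + gain = 0.290 + 0.045 = 0.335, against 0.32 stated.
- Reversion = 2.5% of all subjects, or 0.025/0.315 = 7.9% of those with baseline MS, against 1% stated.

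**Step 3: what the stated assumptions imply.** Take baseline 0.30, end 0.32 and 1% reversion, reading the 1% both ways.

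- 1% of all subjects: loss = 0.010, gain = 0.010 + 0.020 = 0.030, p11 = 0.30 − 0.010 = 0.290, h = 0.040.
- 1% of those with baseline MS: loss = 0.01 × 0.30 = 0.003, gain = 0.023, p11 = 0.297, h = 0.026.

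Neither reading gives 0.070. The first reproduces p11 = 0.290.

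**Step 4: power under each table.** Same method, n = 500. The last column was searched in steps of 10.

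| Table | Baseline / end | h | p11 | Power at n = 500 | Pairs for 80% |
|---|---|---|---|---|---|
| Inputs listed in 8.3 | 31.5% / 33.5% | 0.070 | 0.290 | 80.2% | about 500 |
| h kept, baseline restored | 30% / 32% | 0.070 | 0.275 | 80.1% | about 500 |
| 1% of all subjects revert | 30% / 32% | 0.040 | 0.290 | 93.2% | about 320 |
| 1% of baseline MS revert | 30% / 32% | 0.026 | 0.297 | 97.7% | about 240 |

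A normal approximation shows the same pattern. Power = Φ(0.03/√((h − D²)/n) − 1.645) gives 81.5%, 95.8% and 99.5% at h = 0.070, 0.040 and 0.026.

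The second row separates the two faults. Changing p11 from 0.290 to 0.275 restores 30% and 32% and leaves power essentially unchanged. The difference between 80% and 93% or 98% comes from h, that is, from the reversion assumption.

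**The case against.** The strongest defence is that h = 0.070 is itself a stated input and that 80% is the right power for it. That stands. It also stands that h = 0.070 does not by itself contradict a 30% baseline or a 2-point rise: with p11 = 0.275 all three hold together. Within section 8.3 the slip is therefore in p11, which has almost no effect on power. The conflict over h arises only from the 1% in section 7. The mismatch is also conservative.

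The defence does not rescue section 7. That section gives the 30%, the 2 points and the 1%, does not mention h, and says 500 are necessary for 80% power.

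Three stronger readings go beyond the documents.

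- A reader might infer that the study is under-powered. Power does fall if discordance exceeds 0.070 (71.7% at an assumed h = 0.09), but nothing in the protocol puts h above 0.070, and its own reversion figure puts it lower.
- A reader might infer that 0.070 was taken from the margin scenario, since a 6% gain and a 1% loss give a 5-point rise and h = 0.070. The arithmetic fits, but the protocol does not say so.
- A reader might think the precision of 0.038 at the end of section 8.3 is wrong because about 500 would complete. The sentence refers to the 556 just derived, and 1.96 × √(0.30 × 0.70/556) = 0.0381. The figure is right and is not presented as a Month 12 value.

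**Conclusion.** The inconsistency is real and of moderate weight. D1 = 0.020, h = 0.070 and p11 = 0.290 cannot coexist with a 30% baseline, and the losses they imply cannot coexist with 1% reversion under either reading. Section 8.3's 80% is correct for h = 0.070. Section 7's statement that 500 are necessary is wrong for the assumptions given there, which yield about 93% or about 98% power at n = 500.

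The consequence is a faulty justification, not a faulty study. Under its own reversion assumption the study has more power than it claims. N = 556, the margin, the interval method and the decision rule in section 9.3.1 are unaffected. The power figures rest on Newcombe's method 10, one-sided 5%, a true rise of 2 points and 500 evaluable pairs.

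**What to change.** State one coherent 2x2 table and use it in both sections. Either route works.

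- **(a) Keep h = 0.070, 80% power and N = 556.** In section 8.3 change p11 to 0.275. In section 7 replace the 1% reversion with 2.5% of all subjects (0.025/0.30, about 8% of those with baseline MS). Gains are then 4.5%, and prevalence goes from 30% to 32%.
- **(b) Keep the 1% reversion.** Say whether the denominator is all subjects or those with baseline MS. Set h and p11 to match: 0.040 and 0.290, or 0.026 and 0.297. Restate power at n = 500 as about 93% or about 98%, and remove the statement that 500 are necessary for 80%. Changing h to 0.040 while leaving section 7's present wording would not be enough, because that wording read literally gives 0.026.

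The 0.038 precision needs no change. The cost is wording in sections 7 and 8.3 only, with no change to recruitment or to the analysis.

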9.3.1. Significance and Estimation Test

A bilateral confidence interval of 90% will be calculated for the difference between prevalence rates of the Metabolic Syndrome at study initiation and at study completion (study initiation subtracted from study completion) according to the Newcombe's method (difference between two proportions based on paired data using Newcombe's method 10, 1998c). If, and only if, the upper limit of the confidence interval is lower than the upper limit of the equivalence region $<+ 5\%$, prevalence after the study will be demonstrated to be no worse than prevalence at study initiation.

